10.1.3. Patient population

The patient population for the economic evaluation is the same as defined by the inclusion/exclusion criteria of the clinical trial.

11. Pharmacokinetics

No pharmacokinetics evaluation will be performed in this study.

12. Translational research

Does not apply.

13. Publication policy

The final publication of the study results will be elaborated by the Study Chairman on the basis of the analyses completed at the Data Center.

14. Enrollment and randomization procedures

Patients will be registered in the study via the study website at the time of exam.

15. Forms and procedures for collecting data

Data will be collecting in anonymous form in a database accessible only to the study group.

16. Reporting and evaluation of adverse events

Does not apply.

17. Quality assurance

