21. Trial insurance	15
22. Appendix.....	15
22.1. Definitions	15
22.1.1. WHO performance status scale.....	15
22.1.2. Fleischner's society criteria	16
22.2. Technical Procedures.....	16
22.2.1. Procedure for the pathological review of diagnosis.....	16
22.2.2. Procedures for DTS examination.....	16
22.2.3. Quality of Life evaluation.....	17
22.3. References	19
23. Writing Committee and Scientific support:.....	21

Abbreviations

DTS	Digital Tomosynthesis
CT	Computer Tomography
REID	Risk of Exposure-Induced Death
BEIR	Biologic Effects of Ionizing Radiation
QoL	Quality of Life
OS	Overall Survival
LLE	Loss of Life Expectancy
ROC	Receiver Operating Characteristic
NELSON	The Dutch-Belgian Randomized Lung Cancer Screening Trial (Dutch acronym)
ICH	International Conference On Harmonisation
ECOG	Eastern Cooperative Oncology Group
EORTC	European Organisation for Research and Treatment of Cancer
CRF	Case Record Forms

Synopsis

Sponsor	Santa Croce e Carle Hospital founded by the Fondazione CRC di Cuneo
Project Title	A monocenter prospective no-profit interventional study for lung cancer early diagnosis with tomosynthesis: re-evaluation of lung nodule detection rate at 5 years
Version	July 15 th , 2017
Study Phases	Phase 3
Coordinators	[name] (study chairman), [name] (study coordinator)
Statistician	[name] (University of Torino)
Writing Committee	[name] (Nuclear Medicine Division), [name], [name] (Anatomical Pathology Division), [name], [name] (Medical Phisics Division), [name] (Oncology Division), [name] (Radiology Division), [name], [name], [name] (Thoracic Surgery Division), [name] (Pneumology Division), [name] (Health Management), [name] (Radiotherapy Division).
Population	Subjects enrolled in previously closed SOS trial (high risk subjects for lung cancer) without confirmed lung cancer.
Study Objectives	To evaluate the lung cancer detection rate in the population of high risks subjects previously enrolled in lung cancer screening trial with chest digital tomosynthesis (SOS trial).
Participating centers	Single center, Santa Croce e Carle Hospital

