Sample size	
The primary objective of this study is to calculate the detection rate on lung cancer at 5 years distance from the previous DTS. In the SOS study 1843 subjects were enrolled and lung cancer was found in 18 (0.8%) of them at baseline. 1703 subjects performed the first round DTS at one-year distance and lung cancer was found in 5 (0.3%) of them.
 
The number of patients needed to be confident that the disease will be detected if present at or above the specified prevalence of 0.3% with a confidence of 5% (i.e. assuming that the true prevalence is at least 0.3%, then a sample consisting only of subjects without lung cancer would occur 5% of the time or less given a sample with the calculated size) is 998. Allowing for a drop out of no more than 50%, a minimum number of 1496 subjects is required.

Timelines	
Expected accrual time: September 2017 / August 2018
 
Patients with positive TC will be subjected to diagnostic investigations to identify the pathology according to Fleischner Society. Length of Follow-up: no follow-up is foreseen for these patients

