3.1. Patients inclusion criteria

Inclusion criteria:

- current or former smoker status;
- for former smokers, the maximum time since quitting smoking below 10 years.
- smoking history of at least 20 pack-years;
- age 45-75 years;

- no previous history of cancer in the 10 years before the start of the study;
- be able to stand and hold the breath for 11 seconds during image acquisition
- previous participation to SOS trial

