5.1. Overall survival

Overall survival (OS) defined as the time from randomization until death as a result of any cause (with at least five years of follow-up).

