6.1. Statistical design

6.1.1. Sample size

The primary objective of this study is to calculate the detection rate on lung cancer at 5 years distance from the previous DTS. In the SOS study 1843 subjects were enrolled and lung cancer was found in 18 (0.8%) of them at baseline. 1703 subjects performed the first round DTS at one-year distance and lung cancer was found in 5 (0.3%) of them.

Assuming a binomial model for the occurrence of the disease (Flanders WD and Kleinbaum DG. Basic Models for Disease Occurrence in Epidemiology, International Journal of Epidemiology, Volume 24, Issue 1, 1 February 1995, Pages 1–7) the number of patients needed to be confident that the disease will be detected if present at or above the specified annual incidence of 0.3% with a confidence of 5% (i.e. that assuming the true incidence is at least 0.3%, then a sample consisting only of subjects without lung cancer would occur 5% of the time or less given a sample with the calculated size) is 998. Allowing for a drop out of no more than 50%, a minimum number of 1496 subjects is required.

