10.1. Methods

10.1.1. Type of Economic Evaluation.

Since a predictable variance in effectiveness, a cost-effectiveness analysis is justified.

10.1.2. Choice of Comparator.

The results are compared to the data obtained from the NELSON study and the National Screen Screening Trial for the evaluation of the effectiveness of screening in the control of 10-year mortality due to lung cancer.

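### The economic evaluation compares 10-year lung cancer mortality with external screening trials in a population from which people with known lung cancer have been removed, which favours tomosynthesis

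*Combined protocol and SAP*

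**What the plan says.** The synopsis defines the study population as "Subjects enrolled in previously closed SOS trial (high risk subjects for lung cancer) without confirmed lung cancer". Section 3.1 also requires "no previous history of cancer in the 10 years before the start of the study", and section 14 registers people when they come for the recall exam.

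Section 10.1.3 carries this over to the economic analysis: "The patient population for the economic evaluation is the same as defined by the inclusion/exclusion criteria of the clinical trial". Section 10.1.2 compares the results with two external lung cancer screening trials, "for the evaluation of the effectiveness of screening in the control of 10-year mortality due to lung cancer". Section 10 counts DTS costs arising during the study.

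On the earlier rounds, section 6.1.1 reports: "In the SOS study 1843 subjects were enrolled and lung cancer was found in 18 (0.8%) of them at baseline", and then "1703 subjects performed the first round DTS at one-year distance and lung cancer was found in 5 (0.3%) of them".

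Mortality is listed as an endpoint in the synopsis and in section 2.2, by name only. Follow-up is not consistent. Section 5.1 asks for at least five years for overall survival. The synopsis timelines say, of subjects with a positive CT, "Length of Follow-up: no follow-up is foreseen for these patients". Section 6.3 makes one year after start-up one of the three criteria for ending the study.

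**The concern.** The recall criteria suit the primary endpoint, because only people without known lung cancer can usefully be screened again. They do not suit a mortality comparison. Section 1 describes the external benefit as a reduction in deaths among the high-risk people enrolled in screening trials. The economic population here is what remains of an enrolled cohort after two screening rounds and the years since have taken out those who developed the disease. Its lung cancer mortality before recall is zero by definition.

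At stake is a claim that DTS controls lung cancer mortality as well as, or better than, the external trials, when part of the difference comes from who was left out. Complete vital status or a longer horizon within the eligible group does not bring the excluded people back. The costs do not match either: any mortality effect in this cohort reflects three rounds of DTS, but only the third is costed.

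**Working it through.** The plan gives no lung cancer deaths, no count of cancers between SOS and recall, and no figure for the mortality comparison, so there is no stated result to reproduce on the point itself. Its nearest figures are the SOS yields:

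- 18/1843 = 0.98% (section 6.1.1 prints 0.8%; the synopsis background gives 1.0%).
- 5/1703 = 0.29% (printed as 0.3%).

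The counts are used below, not the percentages.

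**1. Who is excluded.** The hospital has had DTS since March 2010 (synopsis, background) and recall starts in September 2017 (section 6.4), about 7.5 years later. Every cancer found by DTS in SOS therefore falls within the 10-year look-back, as well as under the synopsis population line. Known cases excluded: 18 + 5 = 23, and 23/1843 = 1.25%. An unstated number *I* of cancers between SOS and recall is excluded too.

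**2. Deaths omitted.** Let *f* be the five-year fatality, which is assumed because the documents give neither deaths nor stage for the 23 cases.

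- *f* = 30%: 23 × 0.30 = 6.9.
- *f* = 50%: 23 × 0.50 = 11.5.
- Section 1 gives survival above 70% for early disease. If all 23 were early, the figure is below 6.9.
- Wider assumptions, *I* = 0 to 20 and *f* = 30% to 70%: from 23 × 0.30 = 6.9 to 43 × 0.70 = 30.1 deaths, or 3.7 to 16.3 per 1000 enrolees.

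**3. Share of the cohort's lung cancer deaths omitted, counting from SOS baseline.** Illustrative central inputs: *I* = 10, *f* = 50%, 1496 attenders (the section 6.1.1 minimum), 1% with cancer at recall, then 0.3% new cancers a year. Omitted deaths: 33 × 0.50 = 16.5.

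| Follow-up after recall | Deaths inside the eligible group | Share omitted | Range over assumptions |
|---|---|---|---|
| None | 0 | 100% | – |
| About one year (10% of recall cancers and 5% of new ones fatal) | 1496 × 0.01 × 0.10 + 1496 × 0.003 × 0.05 = 1.72 | 16.5/18.22 = 91% | 56% to 99% |
| Five years (50% and 25% fatal) | 1496 × 0.01 × 0.50 + 1496 × 0.003 × 5 × 0.25 = 13.09 | 16.5/29.59 = 56% | 38% to 80% |

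The ranges vary *I* from 0 to 20, *f* from 30% to 70%, attendance from 998 to 1700 and recall yield from 0.3% to 1.5%. In the one-year row, fatality of recall cancers varies from 5% to 20%. In the five-year row it equals *f*, with half of *f* for new cancers.

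**4. If the clock starts at recall.** No deaths before recall are then due to be counted. The cohort still enters already cleared of cases by two DTS rounds and the following years, and is set against people counted from enrolment in their trials. The selection still lowers its lung cancer mortality.

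**5. Costs.** Assuming every enrolee had the baseline exam, the SOS rounds comprise 1843 + 1703 = 3546 exams. The recall share is 998/(3546 + 998) = 998/4544 = 22.0% if 998 attend, and 1700/(3546 + 1700) = 1700/5246 = 32.4% if the 1700 of section 4 attend.

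**The case against.** The strongest reply is that section 10 opens as a cost comparison between DTS and the CT done in DTS-positive subjects, and the recall population is right for that. This stands for that part of the analysis. It does not cover section 10.1.2, which brings in 10-year lung cancer mortality.

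Second, the economic analysis has no stated time origin. If time runs from recall, starting without known cases is normal for a screening cohort, and zero mortality before recall distorts nothing. This stands as far as omitted deaths go, but the selection in step 4 remains.

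Third, the plan does reach the whole SOS cohort in places: section 4 contacts all participants, the synopsis collects the status of those who refuse the exam, and the sensitivity endpoint counts cancers in the SOS population. None of this overrides the explicit sentence in section 10.1.3, and adding eligible refusers would not restore the cases.

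Three stronger readings are tempting but not supported:

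- **The mortality endpoint itself uses the restricted population.** No population or time origin is stated for it. The restriction is possible there, but it is not written.
- **Almost all lung cancer deaths are left out.** That fits follow-up of none or about one year. Under the five years in section 5.1, the same assumptions give 38% to 80%.
- **Every effectiveness measure is flattered.** The direction applies to mortality. If effectiveness were cancers detected, leaving out the 23 would make DTS look worse.

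**Conclusion.** The concern holds for the economic evaluation. Sections 10.1.2 and 10.1.3 do not fit together: the outcome is lung cancer mortality over 10 years, and the population is selected on not having had the disease. The selection biases the mortality comparison in favour of DTS under either time origin. The exclusion of 23 known cases (1.25% of 1843) follows from the documents. The 7 to 12 deaths among them rest on an assumed fatality of 30% to 50%, and the number is lower if all were early disease. The 22% to 32% cost share rests on attendance of 998 to 1700 and on reading the costed study as the recall round.

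For the mortality endpoint the defect is a different one: its population and time origin are undefined. The primary detection-rate analysis is unaffected. The point should be fixed, because the mortality comparison cannot be interpreted as written, but it concerns a secondary endpoint.

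**What to change.** Change sections 10.1.2 and 10.1.3 in one of two ways:

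- **(a)** Delete the comparison on 10-year lung cancer mortality and report cost per lung cancer found at recall. The population in 10.1.3 can then stay. This is a wording change only.
- **(b)** Compute mortality and economic effectiveness on all 1843 SOS enrolees from the SOS baseline DTS. Include the 23 cases, later cases before recall, non-attenders and the deceased, and count the costs of all DTS rounds.

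Option (b) costs more than wording. Vital status and cause of death must be retrieved and linked, possibly with ethics review: data are held anonymously (section 15), names are not recorded in the database (section 18.2) and registration happens only at the exam. The documents do not show that the sponsor already holds what is needed. The stated mortality will also be less favourable.

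Under either option, state the population and time origin of the mortality endpoint in section 2.2, and reconcile the follow-up statements in section 5.1, section 6.3 and the synopsis timelines. Keep the recall criteria as they are for the detection rate.

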17.1. Control of data consistency

Data forms will be entered in the database by the study assistants.

18. Ethical considerations

18.1. Patient Protection

The responsible investigator will guarantee that this study is led according with either the Declaration of Helsinki and its amendments, and the national, regional and local laws and rules, so to provide adequate protection of the patient.

The protocol has been written, and the trial will be steered according to the ICH Harmonized Guideline for Good Clinical Practice (<http://www.ifpma.org/pdfifpma/e6.pdf>).

The protocol was approved by the Local Ethics Committees

Comitato Etico Interaziendale ASO Santa Croce e Carle di Cuneo

AA.SS.LL. Cuneo1,Cuneo2,Asti.

[name]

[contact]/[name]

Parere Unico n 15-16 del 14/12/2016

Oggetto: "Studio "SOS-Tumore Polmone": diagnosi precoce del tumore polmonare con tomosintesi-ns rif RX10

Codice Protocollo:SOS2

18.2. Subject identification

The name of the patient will not be asked for, nor detailed and recorded in the cloud database. A serial identification number will be ascribed to each patient enrolled into the trial. This number will recognize the patient and must be contained within all the study fans.

18.3. Informed consent

All patients will be learned of the goals of the study, the absence of potential adverse events, the procedures and impending hazards to which he/she will be exposed, and the procedures and algorythm of treatment allocation.

They will be informed as to the strict privacy of their patient data, but that their medical records may be revised for trial purposes by authorized individuals other than their treating physician. A patient informed consent statement is given (in Italian) as an appendix to this protocol (See 22.3.2.). Within the informed consent, it is highlighted that the participation is voluntary and that the patient is permitted to refuse further participation in the protocol whenever he/she wants. This will not prejudice the patient's care in any setting. It is the responsibility of the individual investigator to explain the enclosed informed consent document.

The 'informed consent' form is an essential constituent of the documents and modules needed for protocol submission to the ethics committee for approval.

Documented informed consent must be obtained for all patients included in the study before they are registered or randomized at the Data Center. This must be done in agreement with the national and local regulatory requirements.

The informed consent procedure obeys the ICH guidelines on Good Clinical Practice. This implies that "the written informed consent form should be signed and personally dated by the patient or by the patient's legally acceptable representative".

19. Administrative responsibilities

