DTS	
Acquisition
 
DTS is performed with Discovery XR650 (GE Healthcare, Milwaukee, WI). Images are acquired with a source-to-image distance of 180 cm. The tube voltage is set to 120 kVp with 3 mm Al inherent and 0.2 mm additional Cu filtration. The DTS acquisition consists of 60 projection images along a vertical source path spanning 30° of total tube angular motion. The set of 60 images is acquired in 10 s in breath hold condition. Images are reconstructed at 3 mm plane spacing in the coronal plane. Image reconstruction is done using a filtered back-projection algorithm and a sliding average of seven adjacent planes is taken to reduce noise and low-contrast tomosynthesis artifacts.
 
Dose
 
The mean effective dose expected for DTS is 0.09 ± 0.04 mSv. Based on organ doses the loss of life expectancy (LLE) and the risk of exposure-induced death (REID) are calculated for lung cancer for man and women and for breast cancer for women using BEIRVII[3] model. REID for lung cancer for men and women are 10/100.000 and 3/100.000 respectively. REID for breast cancer for women are 10/100.000. LLE were 0.2 h for men and 0.6 h for women. These values are small respect to the baseline mortality in the normal population that are 7700/100.000 and 4.600/100.000 for lung cancer for men and women and 3.000/100.000 for breast cancer [3].
 
Referral

	Two independent radiologists carry out blinded independent central reviewing for DTS. Discordant and positive cases are discussed in consensus.
Treatment	Subjects are managed in line with Fleischchner Society criteria for the management of small pulmonary nodules and treated using physicians' choice (no indication is given to treatment of patient from this trial).
Radiotherapy	Radiotherapy is performed based on physician's choice (no indication is given to treatment of patient from this trial).

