3.2. Exclusion criteria

[figure not shown]
Exclusion criteria:

- pregnancy

4. Trial Design

During this study, about 1700 subjects, who have been enrolled in SOS Observational Study will undergo a DTS. The study will be presented as an observational clinical trial and registered on clinicaltrials.gov. Initially, all the subjects that participated in the SOS study, will be contacted by phone and invited to perform a DTS in Carle Hospital. When accessing the hospital the subjects will be asked to fill-in a form to confirm that the inclusion criteria of the SOS study are still met. DTS will be then performed and blindly evaluated by two radiologists. DTS findings will be classified based on their dimension (large axis measurement), radiological characteristics (calcific, pleural, solid, partially solid and ground glass opacity) and position (in the 5 lobes). Findings will be then classified using LUNG-RADS[1] schema and ROC analysis will be applied. Inter-observer variability will be analyzed with Krippendorff's Alpha[17].

Discordant and positive cases will be discussed in a consensus session among radiologists and thoracic surgeons. The consensus results will be used in the following analysis. The subjects with one or more nodules larger than 5 mm, not clearly benign, will undergo diagnostic contrast enhanced CT and will be followed in line with Fleischner Society[2].

5. Evaluation criteria

Lung cancer will be histologically proven, following the procedure of Pathology Division that use a double blinded analysis of biological material.

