6.4. Study duration

The start of the study is planned for September 2017. All patients defined by inclusion criteria will be included in the study. The enrollment is done by email. Patients are advised to contact the administrative staff to book an appointment to perform the exam. If the study is completed prematurely, the reasons must be documented. The last patient is expected to enter the study at the end of August 2018.

7. DTS evaluation and revision

Blinded independent central reviewing for DTS.

8. Independent data monitoring committee

This trial will NOT be monitored and scrutinized by an Independent Data Monitoring Committee (IDMC) because no toxicity is expected due to the DTS examination.

9. Quality of life evaluation

Although reducing mortality and morbidity still represent the crucial issue in clinical research, efforts to reduce adverse effects and control symptoms have reached a prominent role in devising therapeutic strategies.

Cancer treatments may produce adverse effects and diminish the QoL even when survival is extended. Progress in the acceptance of new cancer therapies is sometimes critically dependent on their QoL consequences.

Health-related QoL is a multidimensional concept which represents the physiological, psychological and social influences of the disease and the therapeutic process from the patient's perspective. It comprises four principal components: physical, emotional and social well-being, and daily-life functioning.

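### Section 18.3's promise that no adverse events are possible contradicts the hazards named in the same sentence, the Synopsis's DTS radiation risk and the contrast-enhanced CT rule

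*Combined protocol and SAP*

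**What the plan says.** Section 18.3 lists what every subject is to be told, including "the absence of potential adverse events, the procedures and impending hazards to which he/she will be exposed".

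Four other places bear on that sentence.

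- **Synopsis, DTS, Dose.** On lung cancer: "REID for lung cancer for men and women are 10/100.000 and 3/100.000 respectively". On breast cancer: "REID for breast cancer for women are 10/100.000". On loss of life expectancy: "LLE were 0.2 h for men and 0.6 h for women". The Synopsis calls these values small relative to baseline mortality.
- **Section 4, and the design row of the Synopsis.** "The subjects with one or more nodules larger than 5 mm, not clearly benign, will undergo diagnostic contrast enhanced CT".
- **Section 8.** There is no independent data monitoring committee "because no toxicity is expected due to the DTS examination".
- **Section 16.** The section headed "Reporting and evaluation of adverse events" is declared not applicable and has no other content.

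**The concern.** Section 18.3 is the protocol's instruction on what subjects should hear before they agree to take part. To say that adverse events are not even potential is stronger than anything the rest of the protocol supports. The Synopsis quantifies a radiation risk, Section 8 claims only that toxicity from DTS is not expected, and Section 4 adds a second examination with contrast for some subjects. Section 1 itself lists high radiation dose among the drawbacks of CT.

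At stake is the accuracy of the consent provision and, to a lesser degree, whether a reaction at that CT would be recorded anywhere in the study. The estimate of the detection rate is not at stake.

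**Working it through.** The plan gives no calculated figure for this point, so the check compares the texts, with one short calculation for scale.

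**1. The sentence against itself.** It announces that there are no potential adverse events and then that hazards to the subject will be explained. An investigator cannot convey both without qualification.

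**2. The sentence against the Synopsis.** Inputs are the risks of exposure-induced death (REID) in the Synopsis and the planned number in Section 4: "about 1700 subjects, who have been enrolled in SOS Observational Study will undergo a DTS". I take the REID values as applying to one DTS per subject. For women I add the lung and breast values, as deaths from separate causes.

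- Men: 10 per 100,000. Expected deaths per 1700 = 1700 × 10/100,000 = 0.170.
- Women: 3 + 10 = 13 per 100,000. Expected deaths per 1700 = 1700 × 13/100,000 = 0.221.

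The documents do not give the sex mix, so 0.17 (all men) to 0.22 (all women) is the full range.

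Against the baselines of 7700 and 4600 (lung, men and women) and 3000 (breast) per 100,000 in the Synopsis, the ratios are:

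- lung, men: 10/7700 = 0.13%
- lung, women: 3/4600 = 0.07%
- breast, women: 10/3000 = 0.33%

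The Synopsis is right to call the risk small. Small is still not absent.

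**3. The sentence against the CT rule.** Subjects with a nodule above 5 mm that cannot be called benign are directed to a CT with contrast. The only safety rationale in the protocol, in Section 8, concerns DTS. Nothing in the documents supports a claim that the CT carries no potential adverse events. They give neither a CT dose nor a contrast-reaction rate, so no size can be put on this part.

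**4. Both readings of the term.** If adverse events include late radiation harm, the sentence conflicts with the Synopsis for every subject who has a DTS. If the term means acute toxicity only, the DTS part agrees with Section 8, but the CT remains uncovered. The phrase fails on either reading.

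**5. Section 16.** It excludes adverse events in general, so the section states no process for a reaction at the protocol-directed CT. Section 22.2.4 lists a CT review form, but its contents are not shown.

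**The case against.** The strongest reply is that the same sentence obliges the investigator to explain hazards, that Section 18.3 commits consent to GCP, and that subjects receive the consent form, not the protocol. The sentence also promises information on how treatment is allocated, in a study that allocates none, which suggests text carried over from another trial. All of this stands, and it sets the limit of the point. A reader might infer that subjects were told there was no risk. The documents do not support that, because hazard disclosure is required and the form was not available for review.

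A second reply is that the CT is ordinary diagnostic work-up, so reactions belong to clinical care and Section 16 needs no process. The documents leave this open. Section 20 does not list CT among the funded costs, and the Synopsis leaves management to Fleischner criteria and the physician's choice. On the other side, Section 10 costs the CT and Section 22.2.4 gives it a study form. A reader might therefore see Section 16 as a proven gap in trial safety reporting, but that is not established. The existing form may already record reactions. Nor can one say that later complications would be missed: the Synopsis (Timelines) foresees no follow-up, while Section 22.2.4 lists a follow-up form and Section 4 says that these subjects will be followed.

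Two further inferences should also be resisted.

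- Dividing loss of life expectancy by REID to argue that the dose figures are inconsistent needs a benchmark for life lost per induced death, which the documents do not give. They also do not say which cancers the loss for women covers.
- Projecting the number of CTs from the earlier abnormality rates treats those rates as CT referral rates over a five-year interval, and they are neither.

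**Conclusion.** The statement in Section 18.3 that there are no potential adverse events is wrong as protocol wording and should be corrected. It conflicts with its own sentence, with the quantified DTS risk and with a CT that the protocol directs but its safety rationale does not cover. The DTS risk is small: 0.17 to 0.22 expected induced deaths per 1700, taking the Synopsis figures at face value, with one examination each and an unknown sex mix. The CT risk cannot be sized from the documents.

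The conclusion concerns protocol text only and makes no finding about what subjects were actually told. The Section 16 part is secondary, because its force depends partly on whether the CT counts as a study procedure. The primary detection-rate analysis and the sample size are unaffected.

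**What to change.** **Main change, Section 18.3.** Delete the phrase on absent adverse events. State instead that DTS carries a small radiation risk, as set out in the Synopsis, and that subjects who meet the CT rule face additional radiation and contrast risks. Check that the Italian consent form says the same.

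**Lower priority, Section 16.** Limit the declaration of non-applicability to DTS. Add that immediate reactions at the protocol-directed CT are noted on the CT review form already listed in Section 22.2.4, if that form does not capture them now, and that they are handled under usual clinical care.

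**Cost.** A wording amendment with ethics notification, slightly longer consent text and minor data entry for subjects sent to CT. Who receives CT, the sample size and the analysis stay as they are.
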